Appendix 10: Mayo Scoring System

A. Mayo Scoring System

| | 0 | 1 | 2 | 3 |
|--|----------------------------|--|---|---|
| Stool frequency [MCS-SF] ^a | Normal | 1 -2 stools above normal | 3 -4 stools above normal | >4 stools above normal |
| Rectal bleeding [MCS-RB] ^a | No blood seen | Streaks of blood less than half the time | Obvious blood with stool most of the time | Blood alone passed |
| Flexible sigmoidoscopy [MCS-ES] ^b | Normal or inactive disease | Mild disease (Erythema, decreased vascular pattern, no friability) | Moderate disease (Marked erythema, absent vascular pattern, friability, erosions) | Severe disease (Spontaneous bleeding, ulceration) |
| Physician's global assessment [PGA] ^a | Normal | Mild disease | Moderate disease | Severe disease |

a (Lewis J. , et al., 2008)

b (Schroeder, Tremaine, & Ilstrup, 1987)

The total MCS equals the sum of all 4 subscores.

The [REDACTED] equals the sum of the MCS-SF, MCS-RB and PGA subscores.

The [REDACTED] (FDA CDER, 2016) equals the sum of the MCS-SF, MCS-RB and MCS-ES subscores.

| | | | |
|------------|------------|------------|------------|
| | [REDACTED] | [REDACTED] | [REDACTED] |
| [REDACTED] | [REDACTED] | [REDACTED] | [REDACTED] |
| [REDACTED] | [REDACTED] | [REDACTED] | [REDACTED] |
| [REDACTED] | [REDACTED] | [REDACTED] | [REDACTED] |
| [REDACTED] | [REDACTED] | [REDACTED] | [REDACTED] |

## VERSION HISTORY

SAP Amendment #	Date	Description of changes
SAP Version V1.0	13-Nov-2020	
SAP Version V 1.1	27-Jan-2021	Section 6.1.1: Updated derivation of Duration of UC (years)
SAP version 2.0	14-jun-2021	Several updates including analysis and derivation of the primary endpoint.
SAP version 3.0	16-jun-2021	Update typo to sensitivity analysis 1 for primary endpoint and a clarification to the SAS code in the appendix.

## LIST OF ABBREVIATIONS

AE	adverse event
ALT	alanine aminotransferase
ANCOVA	analysis of covariance
AST	aspartate aminotransferase
ATC	anatomical therapeutic chemical
AUC	area under the curve
BLOQ	below lower limit of quantification
BMI	body mass index
CI	confidence interval
CL	clearance
CMH	Cochran-Mantel-Haenszel
CRF	case report form
CRO	contract research organization
CRP	c-reactive protein
CSP	clinical study protocol
CSR	clinical study report
CTCAE	Common Terminology Criteria for Adverse Events
C trough	trough concentration
CTx	serum C terminal telopeptide type I collagen
CV	coefficient of variation
ECG	electrocardiogram
ED	early discontinuation
ES	endoscopy subscore
FAS	full analysis set
FU	follow-up
H	high, above the upper limit of the normal range
HDL	high-density lipoprotein
High	high specificity test
HR	heart rate
hsCRP	high sensitivity C-reactive protein

ICF	informed consent form
ICH	International Council for Harmonization of Technical Requirements for Pharmaceuticals for Human Use
IP	investigational product
IXRS	interactive voice/web response system
L	low, below the lower limit of the normal range
LDL	low-density lipoprotein
LLN	lower limit of the normal range
LLOQ	lower limit of quantification
LRV	lower reference value
LS	least squares
LSM	least square mean
MCII	minimum clinically important improvement
MedDRA	medical dictionary for regulatory activities
MMRM	mixed models for repeated measures
n	number of valid observations
N	normal, with the limits of the normal range
NCI CTCAE	National Cancer Institute Common Terminology Criteria for Adverse Events
NRI	non-responder imputation
OC	observed cases
PASS	patient acceptable symptom state
PGA	physician's global assessment score
PK	pharmacokinetic(s)
PR	pulse rate
q.d.	once daily
QTc	corrected QT interval
QTcF	QT interval corrected for the heart rate using Fridericia's formula
RA	rheumatoid arthritis
RB	rectal bleeding
Reg	regular test
RR	respiratory rate

SAE	serious adverse event
SAP	statistical analysis plan
SD	standard deviation
SDTM	study data tabulation model
SE	standard error
SF	stool frequency
SI	standard international
SMC	Safety Monitoring Committee
TEAE	treatment-emergent adverse event
TLF	tables, listings and figures
TV	target value
UC	ulcerative colitis
[REDACTED]	[REDACTED]
ULN	upper limit of the normal range
ULOQ	upper limit of quantification
[REDACTED]	[REDACTED]
WHO	World Health Organization

## 1. INTRODUCTION

This statistical analysis plan (SAP) describes the final statistical analysis of study GLPG3970-CL-210. The results of the analysis will be described in the clinical study report (CSR).

Technical details on derivations and mock tables, listings and figures (TLFs) will be presented in a separate document.

The statistical analysis will process and present the results following the International Council for Harmonization (ICH) standards, particularly the ICH-E3, ICH-E6, ICH-E9, ICH-R9 (R1) and ICH-E14 guidelines.

## 2. STUDY DESIGN AND OBJECTIVES

### 2.1. Study Objectives

#### 2.1.1. Primary Objective

- To evaluate the effect of GLPG3970 compared to placebo on the signs and symptoms of ulcerative colitis (UC) in subjects with moderately to severely active UC.

#### 2.1.2. Secondary Objectives

- To evaluate the safety and tolerability of GLPG3970 compared to placebo in subjects with moderately to severely active UC.
- To characterize the pharmacokinetic (PK) of GLPG3970 in subjects with moderately to severely active UC.

#### 2.1.3. Other Objectives

+

■

### 2.2. Study Endpoints

#### 2.2.1. Primary Endpoint

- Change from baseline in total Mayo Clinical Score (MCS) at Week 6.

#### 2.2.2. Secondary Endpoints

- Number, incidence, and severity of treatment-emergent adverse events (TEAEs).
- Observed GLPG3970 plasma trough concentrations ( $C_{trough}$ ).

### 2.2.3. Other Endpoints

This diagram illustrates a 2D convolution operation. The input layer (bottom) consists of 10 rows and 10 columns of black bars. The output layer (top) consists of 10 rows and 10 columns of white bars. A 3x3 square of white bars in the center of the input layer represents the kernel. The stride is 1, and the padding is 1. The output layer has a 3x3 kernel receptive field, indicated by the white bars in the input layer. The diagram shows the convolution process, where the kernel slides across the input with a stride of 1, and the output is produced by the center of the kernel. The padding is 1, so the output layer has the same width and height as the input layer.

## 2.3. Study Design

This is a Phase 2, randomized, double-blind, placebo-controlled, multi-center parallel-group study to evaluating GLPG3970 in adult subjects with moderately to severely active UC. In this study, subjects will receive 1 dose level of GLPG3970 (400 mg once daily [q.d.]).

The study is planned to randomize 30 subjects in a 2:1 ratio (20 subjects planned to receive GLPG3970 and 10 subjects planned to receive placebo).

The study will consist of 3 study periods:

[figure not shown]
- Screening period: up to 5 weeks with 2 study visits, with a maximum of 2 weeks from screening visit 2 until randomization.
- Double-blind treatment period: 6 weeks with 4 study site visits (Days 1, 15, 29, and 43 or early discontinuation [ED]) and 1 telephone call (Day 8).
- Follow-up period: 2 weeks with 1 study visit.

The subjects will be in the study for a duration of a maximum of 13 weeks [screening to follow-up (FU)] and will receive oral GLPG3970 or placebo, as a reconstituted oral solution, once daily (q.d.) for 6 weeks.

Refer to the Schedule of Assessments ([Section 2.5](#)) for further details.

A schematic diagram of clinical study design, procedures and stages is provided in [Figure 1](#).

**Figure 1 Schematic Diagram**

## 2.4. Clinical Study Protocol (CSP) and CSP Amendments

This SAP is based on the protocol version 1.0, dated 02-Jul-2020.

## 2.5. Scheduled of Assessments

The study assessments will be undertaken at time points as specified in the Schedule of Assessments ([Table 1](#)). For detailed instructions on the clinical study procedures, please see the relevant CSP sections and CSP Section 8.1, “Timing of Assessments”.

**Table 1 Schedule of Assessments**

EVENT	SCREENING PERIOD		TREATMENT PERIOD 						FOLLOW-UP PERIOD 
	S1	S2 	1	2	3	4	5	ED 	
Study Visit									Follow-up Visit
Study Day (D) ± Days	-35 to 0		1	8 ± 2	15 ± 2	29 ± 2	43 ± 2		14± 3 after last IP dosing
On-site visit	✓	✓	✓		✓	✓	✓	✓	✓
Telephone call				✓					
Informed consent (Section 8.3 of CSP)	✓								
Inclusion/exclusion criteria (Sections 6.1 and 6.2 of CSP)	✓	✓	✓						
Demographics (Section 8.3 of CSP)	✓								
Medical and smoking history including UC history (Section 8.3 of CSP)	✓								
Physical examination (Section 8.5.3 of CSP)	✓		✓				✓	✓	✓
Body weight and height  (Section 8.5.3 of CSP)	✓		✓		✓	✓	✓	✓	✓
Vital signs (Section 8.5.4 of CSP)	✓		✓		✓	✓	✓	✓	✓
12-Lead triplicate ECG (Section 8.5.5 of CSP)	✓		✓		✓	✓	✓	✓	✓

 On dosing days, all assessments are to be performed within 3 hours predose, unless otherwise specified.

 Subjects must come for the study visits at baseline (Visit 1), Day 15 (Visit 3), and Day 43 (Visit 5) and the early discontinuation (ED) visit, if applicable in the morning in a fasting state (no food intake for at least 8 hours).

 Subjects who discontinue treatment early will be requested to return for an ED visit to complete all Visit 5 assessments and to return for a follow-up (FU) visit 14±3 days after last IP administration.

 The endoscopy procedure will be done at Screening Visit 2 once the other in- and exclusion criteria have been confirmed at Screening Visit 1.

 Height only to be measured at Screening Visit 1.

EVENT	SCREENING PERIOD		TREATMENT PERIOD 1, 2						FOLLOW-UP PERIOD 
	S1	S2 	1	2	3	4	5	ED 	
Study Visit									Follow-up Visit
Study Day (D) ± Days		-35 to 0	1	8 ± 2	15 ± 2	29 ± 2	43 ± 2		14 ± 3 after last IP dosing
QuantiFERON TB Gold test (Section 8.5.2 of CSP)	✓								
SARS-CoV-2 RT-PCR test 	✓		✓	As needed					
SARS-CoV-2 serology test			✓	As needed					
Randomization (Section 6.5.1 of CSP)			✓						
Blood collection									
• Safety (hematology, coagulation, chemistry) (Section 8.5.2 of CSP)	✓		✓ 		✓ 	✓	✓ 	✓ 	✓
• Serology (HBV, HCV, HIV) (Section 8.5.2 of CSP)	✓								
• Pregnancy test serum (all WOCBP females) (Section 8.5.2 of CSP)	✓		✓			✓	✓	✓	
• FSH test (WOnonCBP, non-surgical postmenopausal women) (Section 8.5.2 of CSP)	✓								
• PK (Section 8.6 of CSP)			✓ 		✓ 	✓ 	✓ 	✓	

 RT-PCR from a nasal swab sample at screening may be done at an earlier screening visit on a different day than the other screening assessments (after signature of the study informed consent form) and RT-PCR from a nasal swab sample and serology testing at a visit on Day -3, and throughout the study as needed when subject presents signs and symptoms of SARS-CoV-2 infection.

 Fasted glucose, fasted insulin, and HOMA-IR only at baseline (Visit 1), Day 15 (Visit 3), and Day 43 (Visit 5) and the ED visit, if applicable.

 Visit 1: predose (within 30 minutes prior to dosing), 1 sample within [0.5-1.5 hours postdose]; 1 sample within [2-2.5 hours postdose] and 1 sample within [3-4 hours postdose].

 Visit 3 and 4: predose (within 30 minutes prior to dosing).

 Visit 5: 1 sample predose (within 30 minutes prior to dosing) and 1 sample within [4-6 hours postdose].

EVENT	SCREENING PERIOD		TREATMENT PERIOD 1, 2						FOLLOW-UP PERIOD 
	S1	S2 	1	2	3	4	5	ED 	
Study Visit									Follow-up Visit
Study Day (D) ± Days		-35 to 0	1	8 ± 2	15 ± 2	29 ± 2	43 ± 2		14 ± 3 after last IP dosing
Urine collection									
• Safety  (Section 8.5.2 of CSP)	✓		✓		✓	✓	✓	✓	✓
Stool sample collection 	✓		✓		✓	✓	✓	✓	
• Microbiology	✓								
• Microbiome (sampling before IP administration) (Section 8.7.3.2 of CSP)			✓				✓	✓	

 [REDACTED]

 On dosing days, safety urine samples will be taken predose, on the same visit day. Visit 1 and 5: predose and 2 hours postdose. Calcium and phosphate should only be evaluated at Visits 1 and 5.

 At Screening Visit 1, a stool sample should be collected during the visit. If not possible, the subject can collect the sample at home within 24 hours after start of Screening. For Visits 1, 3, and 4, stool samples can be collected within 24 hours prior to the visit or during the visit. At Visit 5 (Day 43) and ED visit, if applicable, when the stool sample must be taken before the bowel preparation for endoscopy, stool can be collected more than 24 hours before the visit. One sample can be used for different assessments.

EVENT	SCREENING PERIOD		TREATMENT PERIOD 1, 2						FOLLOW-UP PERIOD3						
	S1	S2 	1	2	3	4	5	ED 							
Study Visit									Follow-up Visit						
Study Day (D) ± Days		-35 to 0	1	8 ± 2	15 ± 2	29 ± 2	43 ± 2		14± 3 after last IP dosing						
Endoscopy															
Mayo Clinical Score subscores (MCS-SF, MCS-RB, PGA) (Section 8.4.3 of CSP)			✓	✓		✓	✓	✓							
Subject diary evaluation (Section 8.8.1 of CSP)			✓	✓	✓	✓	✓	✓	✓						
Allocation and dispensing of IP supplies (Section 7.2 of CSP)				✓	✓	✓	✓								
IP administration (Section 7.2 of CSP)			Once daily throughout the treatment period 												
Prior and concomitant medication (Section 6.3.2 of CSP)	Throughout the study														
Adverse events (Section 8.5.1 of CSP)	Throughout the study														

 Central endoscopy reading, [REDACTED].

 Screening endoscopic assessment (either surveillance colonoscopy or flexible sigmoidoscopy) should be completed prior to Day -8.

 On Visit 1, 3, 4, and 5, administration of IP must occur at the site.

[figure not shown]
## 2.6. Sample Size Justification

A sufficient number of subjects with UC will be screened in order to have 30 subjects randomized (20 planned subjects on GLPG3970 and 10 planned subjects on placebo).

The 30 subjects randomized in the study, are expected to be sufficient to provide preliminary insight in the safety, tolerability and PK of GLPG3970 in UC patients. In case of drop-outs due to SARS-CoV-2 infection, additional subjects may be randomized on top of the planned sample size. The number of additional subjects randomized will not exceed the number of subjects dropping out of the study in relation to SARS-CoV-2. Randomization of additional subjects will ultimately be decided by the sponsor before any study lock or related unblinding has occurred.

For the efficacy objective, the operating characteristics of the chosen decision framework for the most important endpoint (MCS change from baseline at Week 6) at a sample size of 30 subjects (10 on placebo and 20 on GLPG3970) are represented in the following graph and table, and were deemed acceptable. A common standard deviation of 3.3 was assumed in this small study. Lower Reference Value and Target Value for the decision framework were determined based on the published studies and the therapies in development or on the market. They were identified by the project team as the lowest delta of possible interest and the best case scenario for efficacy outcome respectively.

True Treatment Difference In MCS Change From Baseline At Week 6	Signal Score	Probability Of Outcome
-3.0	Signal detected	0.673
	No conclusion	0.220
	No signal detected	0.107
-1.3	Signal detected	0.205
	No conclusion	0.289
	No signal detected	0.506

## **2.7. Randomization and Blinding**

### **2.7.1. Randomization**

At screening, subjects will be assigned a subject identification number. When a subject is confirmed to be eligible for the clinical study, the subject will be randomized at visit 1.

Allocation of each subject to a given treatment will be done using a centralized electronic system (interactive voice/web response system [IXRS]). Investigational product (IP) will be randomized in a 2:1 ratio to GLPG3970 or placebo.

### **2.7.2. Blinding and Unblinding**

This is a randomized, double-blind clinical study. The subjects and the entire clinical study team, including the investigators, clinical study coordinators, and sponsor personnel are blinded to treatment assignment.

Blinded and packaged medication will be provided to the site. All IP formulations will be identical in appearance, shape, smell and taste and will be packaged in the proper proportion to assure desired dosages and maintenance of the blinding.

The blind can be broken by the investigator for the safety of a subject. The investigator is encouraged to discuss considerations to break the blind with the medical leader, whenever possible and where the situation allows. However, the responsibility to break the treatment code in emergency situations resides solely with the investigator. The investigator is not required to discuss unblinding beforehand if he or she feels rapid emergency unblinding is necessary, but is required to inform the sponsor in within 24 hours after unblinded has occurred.

The blind can be broken by the investigator via IXRS by the investigator.

If the blind is broken for any reason during the course of the clinical study, the moment on which the blind was broken and all other relevant information will be documented by the study site. The reason for breaking the blind will be indicated and justified in the source documentation.

If an AE leads to unblinding, the AE will be given as the reason for unblinding. All subjects who are unblinded should, where possible, complete the follow-up visit assessments  $14\pm3$  days after unblinding. Any AEs will be followed until resolution.

The code-break information (via IXRS vendor) will be provided to the bioanalytical laboratory responsible for PK sample analysis, the person responsible for providing unblinded data to the internal safety monitoring committee (SMC), to the pharmacovigilance vendor for serious adverse event (SAE) reporting purposes, and, if applicable, to the contract research organization (CRO) performing population PK/PD analyses.

### 3. STUDY ESTIMANDS

Estimand for the primary study objective:

Attribute	Details
Treatments	GLPG3970 (400 mg q.d.) vs. Placebo
Population	

Population target defined through the inclusion/exclusion criteria (see CSP).

Analysis Set: Full Analysis Set (FAS) defined as all randomized subjects who have received at least 1 dose of IP.

Endpoint	Change from baseline in total MCS at Week 6.
Population-level summary	Difference (GLPG3970 minus placebo) in least square means (LSM). For further details see study SAP section 6.2.2.2 .
Intercurrent events and strategies to handle those	

Early treatment discontinuation (for any reason) is handled using the hypothetical strategy

Other intercurrent events (e.g. major protocol violations, intake of prohibited medication, lack of compliance) are handled using the treatment policy strategy (i.e. they are ignored)

Estimand for the secondary study objective:

Attribute	Details
Treatments	GLPG3970 (400 mg q.d.) vs. Placebo
Population	

Population target defined through the inclusion/exclusion criteria (see CSP).

Analysis Set: Safety Analysis Set, defined as all subjects who were administered study drug at least once.

Endpoint	Presence of TEAE
Population-level summary	Percentage of subjects with TEAEs.
Intercurrent events and strategies to handle these	

Early treatment discontinuation (for any reason): handled using the while-on-treatment strategy.

Other intercurrent events (e.g. major protocol deviations, intake of prohibited/rescue medication, lack of compliance): handled using the treatment policy strategy (i.e. adverse events are counted regardless the occurrence of these other events).

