9.3.5.2. Adverse Events

Clinical and laboratory AEs will be coded using the latest version of the Medical Dictionary for Regulatory Activities. System Organ Class, High-Level Group Term, High-Level Term, Preferred Term, and Lower-Level Term will be attached to the clinical database.

The following AEs will be considered as TEAEs:

Any AE with an onset date on or after the IP start date and no later than 14 days after last dose of IP, or any worsening of any AE on or after the IP start date. Investigators are not obliged to actively seek SAEs after the CSP defined follow-up period. However, if the investigator is informed about SEA that occurs at any time after the subjects post-treatment follow-up visit and the event is deemed relevant to the use of IP, they should promptly document and report the event to the sponsor by using the SAE form.

Summaries (number and percentage of subjects) of TEAEs per subject by System Organ Class and Preferred Term will be provided by treatment group. TEAEs will also be summarized by causal relationship to the IP and severity. In addition, TEAEs leading to ED of the IP will be summarized and listed. Also, all SAEs, including the non-treatment-emergent SAEs, will be listed.

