#### 6.3.1.1. Definition of Treatment-Emergent Adverse Events

The analysis of AEs will be based on treatment-emergent events (TEAE). TEAEs are defined as

- Any AE with an onset date on or after the IP start date and no later than 14 days after last dose of IP, or any worsening of any AE on or after the IP start date.
- Improvement or no change of any ongoing AEs on or after the IP start date are not considered treatment-emergent. If an AE is ongoing at the time of first IP intake, if there is no change or an improvement in its toxicity grade or its seriousness status (reported in the 'Change in Adverse event details Entry' CRF page), this AE will not be considered as treatment-emergent.

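### SAP 6.3.1.1: coded literally, an 'or' excludes ongoing AEs that worsen only in grade or only in seriousness; SAP 3 also leaves its while-on-treatment strategy undefined

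*SAP*

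**What the plan says.** **TEAE definition.** The first bullet of SAP 6.3.1.1 counts "Any AE with an onset date on or after the IP start date and no later than 14 days after last dose of IP", and also "any worsening of any AE on or after the IP start date". Protocol 9.3.5.2 has the same window and the same second limb: "or any worsening of any AE on or after the IP start date". Neither makes an exception for subjects who stop early.

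**Ongoing AEs.** The second bullet of SAP 6.3.1.1 has two sentences. The first says that ongoing AEs that improve or do not change are not treatment-emergent, which agrees with the definition. The second turns this into a working rule and names the CRF page that supplies the data. An AE ongoing at first intake is not treatment-emergent "if there is no change or an improvement in its toxicity grade or its seriousness status".

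**Safety estimand.** In SAP 3, the endpoint for the secondary objective is "Presence of TEAE", summarised as the percentage of subjects with TEAEs. The first intercurrent-event entry reads "Early treatment discontinuation (for any reason): handled using the while-on-treatment strategy". The second applies treatment policy to all other intercurrent events and explains that "adverse events are counted regardless the occurrence of these other events". The SAP does not define while-on-treatment.

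**Where these feed in.** Under SAP 6.3.1.8 the AE tables show TEAEs, and AEs that are not treatment-emergent are only listed. In SAP Table 2 the treatment analysis period ends at last contact, not at last dose.

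**The concern.** The main issue is the last *or* in the working rule. A programmer who codes that sentence literally will flag an AE as not treatment-emergent as soon as one of the two attributes has failed to worsen. An AE that goes from Grade 1 to Grade 3 but stays non-serious would leave the TEAE tables. So would one that becomes serious at an unchanged grade. The definition two sentences earlier, and the protocol, both call these TEAEs.

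The rule will have data to act on. AEs are recorded from consent (Protocol 11.3.1), and screening lasts up to 5 weeks and includes an endoscopy with biopsies. Worsening of the target disease can be an AE (Protocol 11.1.1), and changes in intensity must be recorded (Protocol 11.2.3). Incidence and severity of TEAEs is a secondary endpoint.

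The lesser issue is the estimand's wording. Without a definition, a reader cannot tell whether an AE that starts a few days after an early discontinuer's last dose counts towards the percentage.

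**Working it through.** No stated figure is at issue, so there is none to reproduce. The check is a logical enumeration plus a comparison of counting windows.

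**1. The 'or' rule.** Let grade and seriousness each be better, same or worse than at first dose, giving 3 × 3 = 9 combinations.

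- Definition (any worsening): a TEAE if either attribute is worse. The combinations with neither worse number 2 × 2 = 4, so 9 − 4 = 5 are worsening combinations.
- Literal *or*: excluded if grade is not worse or seriousness is not worse. Only worse/worse escapes, so 8 of 9 are excluded.
- With *and*: excluded if neither is worse, so 4 of 9.

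| Grade | Seriousness | Definition | Literal *or* | With *and* |
|---|---|---|---|---|
| worse | same | TEAE | excluded | TEAE |
| worse | better | TEAE | excluded | TEAE |
| same | worse | TEAE | excluded | TEAE |
| better | worse | TEAE | excluded | TEAE |
| worse | worse | TEAE | TEAE | TEAE |
| other four | (neither worse) | not TEAE | excluded | excluded |

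The literal rule conflicts with the definition in 4 of the 5 worsening combinations; the *and* rule conflicts in none. There is also a middle reading, in which no change must hold for both attributes but improvement in either one is enough to exclude. It still conflicts in 2 of 5: better/worse and worse/better. These are counts of logical cases, not expected shares of events.

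**2. Leverage of one subject.** The planned arms are 20 and 10. One subject whose only TEAE is misclassified moves the percentage by 1/20 = 5 points on GLPG3970 or 1/10 = 10 points on placebo.

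**3. The estimand wording, on the strict reading only.** Suppose while-on-treatment ended at last dose. It would then apply to early discontinuers alone, because early discontinuation is the intercurrent event concerned.

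| Last dose | Days to last dose | TEAE window (+14) | Share lost |
|---|---|---|---|
| Day 8 | 8 | 22 | 14/22 = 64% |
| Day 15 | 15 | 29 | 14/29 = 48% |
| Day 29 | 29 | 43 | 14/43 = 33% |

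A completer dosed to Day 43 would keep all 43 + 14 = 57 days.

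The documents give no TEAE risk. As an illustration, assume a constant hazard and a risk r over 57 days. The chance of a counted TEAE over d days is then 1 − (1 − r)^(d/57). For a Day 15 stop:

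| Assumed r | d = 29 (6.3.1.1) | d = 15 (strict) |
|---|---|---|
| 30% | 16.6% | 9.0% |
| 50% | 29.7% | 16.7% |
| 70% | 45.8% | 27.2% |

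**4. Does the SAP apply the strict reading anywhere?** SAP 6.3.1.1 has no exception for early discontinuers. SAP 6.3.1.3 allocates AEs by start date to a treatment period that runs to last contact. SAP 6.3.1.8 tabulates TEAEs with no cut at discontinuation. Early discontinuers are asked back 14 ± 3 days after last dose, so the events are collected. The strict reading is therefore not carried out in any derivation or table rule.

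**The case against.** **On the 'or'.** In ordinary English, no change or improvement in A or B can mean that neither A nor B got worse. The sentence before it and the first bullet both point that way, so the intent is not in doubt. An AE that worsens on both attributes stays a TEAE even on the literal reading. Nothing is lost from the record either: changes in AE attributes are captured and linked (SAP 6.3.1), all AEs are listed with a treatment-emergent flag, and SAEs have their own listing. All of this stands, and it limits the harm to the tables. It does not remove the faulty sentence, which is the one written for programming. The charitable reading also fits the improvement limb poorly, as the middle reading in the working shows.

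**On the estimand.** A reader might infer that SAP 3 contradicts the TEAE definition by ending the count at last dose, and that the comparison therefore favours the less well tolerated arm. The documents do not support going that far. The endpoint is itself presence of a TEAE, which brings in the 14-day window, and the SAP's treatment period runs past last dose. While-on-treatment can coherently mean follow-up to each subject's own last dose plus 14 days, the same for completers and early stoppers. What remains is the contrast with the next bullet, where AEs are counted regardless of the event. That gives the strict reading some support, enough to make the wording ambiguous but not to make it a stated counting rule.

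**Conclusion.** The *or* in the second bullet of SAP 6.3.1.1 is a real drafting fault. Taken literally, it reverses the definition in 4 of the 5 worsening combinations for AEs ongoing at first dose, against the same section's first bullet and Protocol 9.3.5.2. The intended rule is clear from the neighbouring text, so the consequence is a risk of misprogramming, not a demonstrated error in results. How many subjects it would touch depends on how many AEs are ongoing at first dose and then worsen, which the documents do not give.

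The while-on-treatment entry in SAP 3 is an ambiguity to align. The lost-window shares (64%, 48%, 33%) hold only on the strict reading, and the probabilities also need the assumed risk and constant hazard. No unconditional claim of bias between arms follows.

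Both points concern descriptive safety summaries with no formal testing. The primary efficacy analysis and the sample size are unaffected. The change is worth making because a secondary endpoint depends on this flag and the correction costs almost nothing.

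**What to change.** 1. In the second bullet of SAP 6.3.1.1, change the exclusion condition to: no worsening in toxicity grade **and** no worsening in seriousness status. This gives zero conflicts with the definition.
2. In SAP 3, keep the while-on-treatment label in the early-discontinuation entry for the safety estimand and add: *(AEs counted up to 14 days after last dose, as in 6.3.1.1)*. If the sponsor does mean to stop counting at discontinuation, SAP 3 should say so and give the reason, and the definition in SAP 6.3.1.1 and Protocol 9.3.5.2 must be reconciled with it.

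The cost is two wording edits, plus a check of one condition in the TEAE flag in case the literal *or* has already been programmed. No new data, tables or analyses are needed.
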